9.3 Safety Blood Collection

Patients who experience a serious or severe AE should have, at the discretion of the Investigator, a blood sample drawn for safety labs as soon as possible after the AE has occurred.

Additional blood sampling may be performed at any time during the study if warranted to monitor patient safety.

9.4 Pregnancy

Pregnancy in a patient or partner should be reported within 24 hours of the site becoming aware of the pregnancy by fax or email of the Pregnancy Reporting Form in the study reference materials to Catalyst. In addition, pregnancy in a patient is also reported on the End of Study CRF. The Investigator must make every effort to follow the patient through resolution of the pregnancy (delivery or termination) and to report the resolution on the follow-up form (Pregnancy Reporting Form: Additional Information) in the study reference materials. In the event of pregnancy in the partner of a study patient, the Investigator should make every reasonable attempt to obtain the woman's consent for release of protected health information.

9.5 Urgent Safety Measures

The regulations governing clinical trials state that the sponsor and Investigator are required to take appropriate urgent safety measures to protect subjects against any immediate hazards that may affect the safety of subjects, and that the appropriate regulatory bodies should be notified according to their respective regulations. According to the European Union (EU) Clinical Trial Directive 2001/20/EC, "...in the light of the circumstances, notably the occurrence of any new event relating to the conduct of the trial or the development of the investigational medicinal product where that new event is likely to affect the safety of the subjects, the sponsor and the Investigator shall take appropriate urgent safety measures to protect the subjects against any immediate hazard. The sponsor shall forthwith inform the competent authorities of those new events and the measures taken and shall ensure that the IRB/IEC/REB is notified at the same time." The reporting period for urgent safety measures is the period from the time of signing of the ICF through the completion of the last study visit. Investigators are required to report any urgent safety measures with 24 hours.

	MSK-003	Page 35
---	---------	---------

Examples of situations that may require urgent safety measures include discovery of the following:

- An immediate need to revise IP administration (i.e. modified dose amount or frequency not defined in protocol).
- Lack of study scientific value, or detrimental study conduct or management.
- Discovery that the quality or safety of IP does not meet established safety requirements.

10 APPROPRIATENESS OF MEASUREMENTS

The measures of safety used in this study are routine clinical and laboratory procedures.

The efficacy measure is a self-report on how the patient is functioning for activities of daily living. This standardized test has been previously used for determination of response to therapeutic intervention in patients with MG.

11 STUDY PROCEDURES

11.1 Start of Long Term Study

An ICF for the Long-Term Study must be signed and dated by the patient, the Investigator or designee, and witness (if required) before any study-related procedures are performed.

	MSK-003	Page 36
---	---------	---------

The following procedures are to be performed as scheduled Day 0 and can serve as baseline for the Long-Term study. Any procedure not performed for MSK-002 protocol needs to be completed for this trial.

- Informed Consent for MSK-003;
- Inclusion/Exclusion criteria for the current study must be verified;
- Standard 12-lead ECG after 5 minutes in the supine position;
- Complete physical examination including weight;
- Vital signs (seated position), including SBP, DBP, heart rate, respiration, and body temperature;
- Clinical laboratory tests including hematology, chemistry, and urinalysis;
- Urine pregnancy test in females of childbearing potential only;
- MG-ADL (use data from Day 0 of MSK-002 for all patients);
- AEs;
- Concomitant medications.

11.2 End of Months 3, 6, 9, 12, 15, 21, 27, 33 and 39

The following assessments and procedures will be determined at the end of Months 3, 6, 9, 12, 15 and 21, 27, 33 and 39. Each month has a clinic visit window of \pm 1 week. Additional visits are allowed as necessary.

- Assessment of AEs/SAEs;
- Complete physical exam with weight;
- Vital signs (seated position), including SBP, DBP, heart rate, respiration, and body temperature;
- Standard 12-lead ECG after 5 minutes in the supine position;
- Clinical laboratory tests including hematology, chemistry, and urinalysis;
- Urine pregnancy test in females of childbearing potential only;
- Concomitant medications;
- IP accountability of medication;
- MG-ADL

	MSK-003	Page 37
---	---------	---------

All IP should be collected from the patient at each visit, in order to perform drug accountability. The site will dispense sufficient amifampridine for daily outpatient administration for 90 days (for 180 days on Months 15, 21, 27, 33 and 39). If the Investigator wants to evaluate the patient more frequently, fewer tablets can be dispensed.

Patients may continue to receive amifampridine until the study is terminated, the patient decides to withdraw from the study, or the development program is discontinued for this indication.

11.2.1 End of Study Visit

Patients will report to the study site at the end of the study and have the assessments and procedures listed below completed. This visit may be incorporated at the scheduled 3-or 6-month visit.

- Assessment of AEs/SAEs;
- Complete physical exam with weight;
- Vital signs (seated position), including SBP, DBP, heart rate, respiration, and body temperature;
- 12-Lead ECG;
- Clinical laboratory tests;
- Urine pregnancy test in females of childbearing potential only;
- Concomitant medications;
- IP accountability;
- MG-ADL

12 DATA QUALITY ASSURANCE

Catalyst personnel or designees will visit or telephone the study site before initiation of the study to review with the site personnel information about the IP, protocol and other regulatory document requirements, source document requirements, CRFs, monitoring requirements, and procedures for reporting AEs/SAEs.

At visits during and after the study, a CRA will monitor the site for compliance with regulatory documentation, with a focus on accurate and complete recording of data on CRFs

	MSK-003	Page 38
---	---------	---------

from source documents, adherence to protocol, AE/SAE reporting, and drug accountability records. The CRA will also verify records at the site pharmacy.

13 STATISTICAL METHODS AND DETERMINATION OF SAMPLE SIZE

13.1 Statistical and Analytical Plans

13.1.1 Interim Analyses

No interim analyses are planned.

13.2 Analysis Populations

The analysis population in this study is the safety population and will consist of all patients who are enrolled in the Long-Term study and have received at least one dose of amifampridine. Safety evaluation from MuSK-MG and AChR-MG groups will be analyzed separately.

13.3 Primary Endpoint

The primary endpoint of the study is safety and tolerability of amifampridine at Months 3, 6, 9, 12, 15 and 21, 27, 33 and 39. For more details see Section [13.5](#) below.

13.4 Secondary Endpoint

The secondary endpoint of the study is the MG-ADL score at Months 3, 6, 9, 12, 15, 21, 27, 33 and 39.

13.5 Safety Analysis

Prior to analysis, all AEs will be coded using the MedDRA coding dictionary. Based on these coded terms, TEAEs and SAEs will be summarized using system organ class and preferred terms, as well as by relationship to treatment. All AEs will be listed, regardless of whether they were study treatment related.

Vital signs will be summarized using descriptive statistics (mean, standard deviation, median, minimum, maximum, and number of non-missing observations) by time point. Changes from baseline will also be summarized by post-dose time point.

Clinical laboratory parameters will be summarized using descriptive statistics (mean, standard deviation, median, minimum, maximum, and number of non-missing observations) by time point. Changes from baseline will also be summarized by post-dose time point. In

	MSK-003	Page 39
---	---------	---------

addition, a shift table will be constructed to show the shifts in laboratory results by parameter relative to the normal ranges. The number and percentage of subjects with the following shifts will be presented: normal/normal, normal/low, normal/high, low/low, low/normal, low/high, high/low, high/normal, and high/high. Similar shift tables will also be constructed for physical exam results. ECG results will be summarized in a shift table with the following shifts presented: normal/normal, normal/abnormal, abnormal/normal and abnormal/abnormal. A table of descriptive statistics for QTc will be created.

Additional safety analyses may be performed as described in the SAP for the study.

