8.2.2 Exclusion Criteria

Individuals who met any of the exclusion criteria in the original protocol or those listed below are not eligible to participate in the study:

1. Epilepsy and currently on medication.
2. Clinically significant abnormalities in 12 lead ECG, in the opinion of the Investigator.
3. Breastfeeding or pregnant at Screening or planning to become pregnant at any time during the study.
4. Intolerable amifampridine-related side effects
5. Treatment with an investigational drug (other than amifampridine) or device while participating in this study.
6. Any medical condition that, in the opinion of the Investigator, might interfere with the patient's participation in the study, poses an added risk for the patient, or confound the assessment of the patient.

	MSK-003	Page 22
---	---------	---------

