8.6.5 Electrocardiogram (ECG)

A standard 12-lead safety ECG (single tracing) will be recorded with the patient resting comfortably in the supine position at the time points specified in the Schedule of Events ([Table 1](#)) and in Section 11. Clinically significant changes from baseline will be recorded as AEs.

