3.3 Safety Analysis

3.3.1 *General*

All safety summaries will be presented overall for the safety population. The evaluation will take into account the recorded adverse events (AE), clinical laboratory tests, vital signs, physical exam, ECG assessments and concomitant medications.

3.3.2 *Adverse Events*

Since patients started taking study medication before enrolled the study, all AE reported are considered as treatment-emergent adverse events (TEAE).

Tabular summaries will be provided by indication for the number and percentage of patients with:

- Any TEAE by SOC and PT. This summary will include the number of unique events reported.
- Any study drug-related TEAE by SOC and PT
- Any TEAEs by SOC, PT and maximum severity
- Any treatment-emergent serious adverse event (TESAE) by SOC and PT
- Any TEAE that results in patient discontinuation from the study by SOC and Preferred Term (PT)

A listing of all adverse events will be provided. In addition, separate data listings will be presented for the following:

- Patient deaths

- Serious Adverse Events (SAEs)
- Listing of Grade 3 (Severe) or Grade 4 (Life-threatening) AEs
- Listing of AEs leading to study discontinuation

3.3.3 *Vital Signs*

A summary of values and changes from Baseline will be provided by vital signs parameter and visit of at 3, 6, 9, 12, 15, 21, 27, 33 and 39 months.

3.3.4 *Electrocardiogram (ECG)*

Each over-read ECG interval and change from baseline in each interval will be summarized descriptively by visit at 3, 6, 9, 12, 15, 21, 27, 33 and 39 months

Treatment-emergent cardiac abnormalities, as well as the overall interpretation, will be summarized. Treatment-emergent ECG findings considered by the investigator to be clinically significant will be presented only in a listing.

3.3.5 *Clinical Laboratory Assessments*

A summary of laboratory values and changes from Baseline will be provided by test and visit of at 3, 6, 9, 12, 15, 21, 27, 33 and 39 months. In addition, laboratory measures out of range or abnormal will be presented for each visit. Values deemed clinically significant by the Investigator will not be summarized, but will be presented in a listing.

3.3.6 *Physical Examinations*

The number and percent of patients with physical examination abnormalities will be summarized by body system and visit of at 3, 6, 9, 12, 15, 21, 27, 33 and 39 months.

3.3.7 *Concomitant Medications*

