3.5 Key Data Items

Study Analysis Population Definition:

- All Subjects: All subjects, including screening failures, who provided clinical information in the database.
- Safety Population: All enrolled subjects who receive at least one dose of study drug.

Important Derived Variables:

- Age (in year) = (Screening Date – Date of Birth +1)/365.25.
- Prior Medications and Treatments: The medications and treatments started before enrolled to the study (date of Informed Consent signed)
- Concomitant Medication and Treatments: The medications and treatments started on or after the date of Informed Consent signed
- Baseline: All safety measurements collected at Day 1 or before the first dose of study drug will be used as baseline
- Post Baseline Visit: follow up visit of 6, 9, 12, 15, 21, 27, 33 and 39 months after baseline and etc, or unscheduled visit after first dose of the study drug
- Study Day for follow-up visit: The visit date – Baseline date +1
 - o Follow-up visit at 3 months: The visit that is closest to study day 91
 - o Follow-up visit at 6 months: The visit that is closest to study day 183
 - o Follow-up visit at 12 months: The visit that is closest to study day 365
 - o Follow-up visit at 15 months: The visit that is closest to study day 456
 - o Follow-up visit at 21 months: The visit that is closest to study day 640
 - o Follow-up visit at 27 months: The visit that is closest to study day 822
 - o Follow-up visit at 33 months: The visit that is closest to study day 1005
 - o Follow-up visit at 39 months: The visit that is closest to study day 1187
- Duration of Disease (year):
(Date of Informed Consent signed – Date of original Diagnosis +1) / 365.25
- Study drug compliance (%): $100 \times \text{Total Dose (mg)} / \text{Total Prescribed Dose (mg)}$, where total dose taken will be calculated as (Dispensed # - Retuned # - Lost #) $\times 10$ mg (refer to CRF IP Accountability page (DA domain), and the total prescribed dose is collected at each IP accountability CRF (EX domain))
- Treatment emergent Adverse Events (TEAE): All AEs reported in this study are TEAE

Formulas of Metric Conversion:

- 1 inch = 2.54 cm
- 1 lb = 0.4536 kg
- $^{\circ}\text{C} = (^{\circ}\text{F} - 32) \times 5/9$

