4. OUTPUT PLANNED FOR THE STUDY REPORTS

4.1 Tables Planned for Interim Reports and Final Study Report

| Table # | Table Title | CSR | DSUR |
|---------|--|-----|------|
| T01 | Subject Disposition (All subjects) | X | X |
| T02 | Demographics and Baseline Data Summary Statistics (Safety Population) | X | X |
| T03 | Summary of Study Drug Exposure and Compliance (Safety Population) | X | X |
| T06 | Number and Percent of Subjects with Treatment Emergent Adverse Events (Safety Population) | X | X |
| T07 | Summary of Treatment Emergent Adverse Events (Safety Population) | X | X |
| T08 | Number and Percent of Subjects with Treatment Emergent Serious Adverse Events (Safety Population) | X | X |
| T09 | Number and Percent of Subjects with Treatment Emergent Adverse Events by Relationship to Treatment (Safety Population) | X | X |
| T10 | Number and Percent of Subjects with Treatment Emergent Adverse Events of Grade 2 or Higher (Safety Population) | X | X |
| T11 | Serum Chemistry Clinical Laboratory Summary Statistics by Visit (Safety Population) | X | |
| T12 | Hematology Clinical Laboratory Summary Statistics by Visit (Safety Population) | X | |
| T13 | Urinalysis Clinical Laboratory Summary Statistics by Visit (Safety Population) | X | |
| T14 | Serum Chemistry Shift Table by Visit (Safety Population) | X | |
| T15 | Hematology Shift Table by Visit (Safety Population) | X | |
| T16 | Urinalysis Shift Table by Visit (Safety Population) | X | |
| T17 | Vital Sign Parameters Summary Statistics by Visit (Safety Population) | X | X |
| T19 | Summary of ECG by Assessment Category and Visit (Safety Population) | X | |
| T20 | ECG Shift Table by Assessment Category and Visit (Safety Population) | X | |
| T21 | Number and Percent of Subjects Taking Concomitant Medications by ATC Level 3 and Preferred Term (Safety Population) | X | |

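### As specified, the ECG tables cannot show a worsening from a minor to a clinically significant abnormality, and no planned table counts patients with a new clinically significant ECG

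*Protocol*

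**What the plan says.** **The shift table.** Protocol 13.5: "ECG results will be summarized in a shift table with the following shifts presented: normal/normal, normal/abnormal, abnormal/normal and abnormal/abnormal". The same section asks for descriptive statistics on QTc. For laboratory results it specifies a low, normal and high shift table with nine cells.

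**The SAP's ECG outputs.** SAP 3.3.4 summarizes each over-read interval, with change from baseline, by visit. It continues: "Treatment-emergent cardiac abnormalities, as well as the overall interpretation, will be summarized". It then says: "Treatment-emergent ECG findings considered by the investigator to be clinically significant will be presented only in a listing". In SAP 4.1, T19 summarizes ECG by assessment category and visit, and the title of T20 begins "ECG Shift Table by Assessment Category and Visit (Safety Population". The SAP nowhere says what the categories are.

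**Entry.** Exclusion 2 in Protocol 8.2.2 is "Clinically significant abnormalities in 12 lead ECG, in the opinion of the Investigator".

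**The adverse event route.** Protocol 8.6.5, on ECGs: "Clinically significant changes from baseline will be recorded as AEs". SAP 3.5: "All AEs reported in this study are TEAE". SAP 3.3.2 tabulates these by system organ class and preferred term, by relationship to study drug, and as "Any TEAEs by SOC, PT and maximum severity".

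**Status.** SAP 2.2.1 names ECG parameters as a safety endpoint. Protocol 13.3 makes safety and tolerability at the scheduled months the primary endpoint. Protocol 13.7 gives the SAP precedence where the two documents differ on analysis.

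**The concern.** A shift table exists to show who got worse. Patients with a clinically significant ECG abnormality are kept out at entry, so someone whose baseline ECG is abnormal should have a minor abnormality. The change that matters most in that person is from minor to clinically significant, and a table with only normal and abnormal levels has no cell for it. The SAP then directs the clinically significant findings to a listing, so the other ECG tables do not clearly make up for this.

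Cardiac safety is a live question for this drug. The safety summary in Protocol 6.2 reports QTc prolongation and ventricular extrasystoles (2 of 1,454 each), and single cases of supraventricular tachycardia and cardiac arrest. SAP 3.3.2 notes that patients were already on study medication before enrolment, so an abnormal baseline tracing may itself reflect exposure. A reader of the study report would want to see directly how many patients developed a clinically significant ECG, when, and from what starting point.

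**Working it through.** The plan gives no figure on this point, so the check is a mapping of ECG states onto the planned outputs.

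**Step 1: states.** Let N be normal, NCS abnormal but not clinically significant, and CS abnormal and clinically significant. A baseline by post-baseline grid has 3 × 3 = 9 cells. The Protocol 13.5 table has 2 × 2 = 4.

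**Step 2: apply Exclusion 2.** If the baseline tracing is the one used for eligibility, or agrees with it, CS at baseline should not occur. That leaves 2 × 3 = 6 possible transitions, which fall into the four cells as follows.

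| Transition | Protocol 13.5 cell |
|---|---|
| N to N | normal/normal |
| N to NCS | normal/abnormal |
| N to CS | normal/abnormal |
| NCS to N | abnormal/normal |
| NCS to NCS | abnormal/abnormal |
| NCS to CS | abnormal/abnormal |

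Both transitions that end in CS share a cell with one that does not. Neither can be read off the table.

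**Step 3: does the SAP supply other levels?** T19 and T20 refer to assessment categories without defining them, and SAP 3.3.4 gives no levels for the overall interpretation. The two levels in Protocol 13.5 are therefore the only definition on record. If the undefined categories were meant to separate CS from NCS, that would sit badly with the sentence confining CS findings to a listing. On either reading the SAP text needs correcting.

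**Step 4: trace a CS change through the other outputs.**

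| Output | Is the event represented? | What is missing |
|---|---|---|
| TEAE tables T06 to T10 | Yes, through Protocol 8.6.5 and SAP 3.5 (T08 and T10 only if seriousness or grade qualifies) | Visit and baseline ECG status; no single ECG count |
| Interval and QTc summaries | Only if an interval changed, as part of a mean or range | Number of patients with a CS ECG |
| Listings DL06a (adverse events) and DL09 (ECG) | Yes, patient by patient | Not a table |

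Protocol 9.1 prefers a diagnosis to its component signs as the event term, so CS ECGs may also be spread over several preferred terms. Adding up ECG-related terms would not reliably give the number of patients.

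**Step 5: scale.** The documents give neither the share of patients with an abnormal baseline ECG nor an expected rate of new CS ECGs, so the number affected cannot be calculated. They do give planned numbers: up to about 60 MuSK-MG and approximately 10 AChR-MG patients, with safety endpoints analysed by MG type (SAP 3.1.4). One patient is 1/60 = 1.7% of the first group and 1/10 = 10% of the second.

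**The case against.** The strongest reply is that these events are captured and counted elsewhere. A change from minor to clinically significant is exactly what Protocol 8.6.5 requires to be recorded as an adverse event, the SAP treats every adverse event as treatment-emergent, and the tables give numbers and percentages by indication. This stands. A reader might infer from SAP 3.3.4 that clinically significant ECG findings appear in no summary at all; the documents do not support that. What remains is narrower: the adverse event tables cannot show visit or baseline ECG status, and none isolates new clinically significant ECGs.

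Second, the SAP prevails over the protocol's statistical text, and the SAP does not say that T20 has two levels. This also stands in part. One cannot assert that the final table will have only normal and abnormal rows. But precedence helps only where the SAP says something different, and here it says nothing about levels.

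Third, the listing sentence can be read as applying to the investigator's significance flag, with the ECGs themselves still entering the summaries of cardiac abnormalities and intervals. That is plausible. It still leaves the flag, which is what separates minor from significant, out of the tables.

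Fourth, it would be too strong to say that the ECG and adverse event tables cannot be reconciled. With about 70 patients, DL06a and DL09 can be matched by hand; the tables alone do not allow it. Nor does the plan label abnormal/abnormal as no change. That is a natural reading of the cell, not the documents' wording.

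Finally, the study is descriptive and tests no hypothesis, so no estimate or decision rule changes. True, but that makes the quality of the safety displays more important, since they are the main product of the study.

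**Conclusion.** The point holds as a weakness in how a named safety endpoint is displayed. On the only levels the documents define, the ECG shift table merges both transitions to a clinically significant abnormality with transitions that are not, and no planned table states how many patients developed one. The events themselves are recorded, counted as TEAEs and listed, so this is a loss of visibility in the ECG outputs and not a loss of data.

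The conclusion rests on two assumptions: that Exclusion 2 was applied to the baseline tracing, and that T20 follows the protocol's levels because the SAP gives no others. If the first fails, the abnormal/abnormal cell also contains patients who were clinically significant at baseline and is harder still to read. If the second fails, the defect becomes an undefined table that conflicts with the listing sentence.

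The number of patients affected is unknown, and any figure for events obscured would rest wholly on assumed inputs. Because results are shown by MG type, a single patient can matter, above all in the AChR-MG group. This should be corrected before the final tables are produced; it does not threaten the validity of the study.

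**What to change.** In SAP 3.3.4 and T20:

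- Define three levels: normal; abnormal, not clinically significant; abnormal, clinically significant. Use the same definition in T19.
- Present shifts from baseline to each scheduled visit and to the worst post-baseline result, by MG type.
- Add the number and percentage of patients with any post-baseline clinically significant ECG, with the denominator stated. Say whether unscheduled tracings count towards this and towards the worst result, because SAP 3.1.2 otherwise keeps unscheduled data out of summary tables.
- Delete the word *only* from the sentence that confines clinically significant findings to a listing, and keep the listing.

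The cost is SAP wording and minor programming, and the laboratory shift table already uses three levels. One check is needed first. Protocol 8.6.3 requires a clinical-significance comment on each abnormal laboratory result, but Protocol 8.6.5 has no such requirement for each ECG, and the ECG form is not among the documents. The sponsor should confirm that the form records clinical significance for each tracing. If it does not, the three-level table may not be feasible at every visit. In that case, report the count of patients from the clinically significant findings already planned for the listing.
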